5 CORRELATIVE STUDIES FOR RESEARCH

5.1 IMMUNE CELL INFILTRATE (TISSUE SPECIMENS)

Slides made from prostate biopsy specimens (collected at baseline) and prostatectomy specimens (collected at surgery performed after last dose of vaccine) will be stained for CD4 and CD8 cells and digitized for analysis of immune cell infiltrate. Other markers such as CD4/FoxP3 may also be stained for further correlative studies. These studies will be performed by the Laboratory of Tumor Immunology and Biology. At a minimum, 5 slides from one biopsy core confirmed to contain cancer will be needed for baseline quantification. Attempts will be made based on anatomic location notation or when available, MRI based location, to correlate biopsy location with pathologic location on prostatectomy specimens. When feasible, quantitation will be performed in triplicate. Quantitation will be reported as number of stained cells per micron squared of surface area. Wilcoxon matched pair signed rank test, Friedman test with Dunn's multiple comparisons, or alternative statistical models will be used as appropriate. Aperio ScanScope digital scanner systems with Aperio ImageScope software algorithms will be used. Manual quantitation will be performed in case of software malfunction. Isotype antibodies

negative controls will be included in all runs. Tonsil or lymph node tissue will be positive control for CD4 and CD8. Slides will be developed with primary and secondary antibodies per manufacturer specifications for visualization of cells.

Peripheral Blood Correlative Studies for Research/Pharmacokinetic Studies

Blood Studies	Blood Tube/Comments**	Destination
CBC with differential	One light lavender tube	CC Department of Laboratory Medicine (DLM)
Hepatic Panel, Acute Care Panel	One 4 mL SST	CC DLM
Anti-HIV-1/2	One 8 mL SST	CC TTV lab
PT/PTT/INR	One 4.5 mL citrate blue top	CC DLM
HBs Antigen Screening	One 8 mL SST	CC Department of Transfusion Medicine (DTM)
Anti-HCV Antibody	One 4 mL SST	CC DLM
Prostate Specific Antigen	One light lavender tube	CC DLM
Lymphocyte Phenotyping, TBNK	Six 10 mL Na Heparin tubes Two 8 ml SST tubes	NCI-Frederick [name]
Gene expression profiling* lab)	Two 2.5 mL RNA PaxGene tubes	Blood Processing Core ([name]

*RNA PaxGene to be drawn only on the weeks of biopsies or standard of care prostatectomy

** Please note that tubes and media may be substituted based on availability with the permission of the PI or laboratory investigator.

5.1.1 Sera Antibody Analysis

Serum will be stored at -80 degrees Celsius and there will be planned analysis for generation of antibodies to PSA, BCG, PAP, PSMA, PSCA, and/or MUC-1 by the Laboratory of Tumor Immunology and Biology.

Table 1. Preliminary Data from a trial of Prostvac in mCRPC. This table shows how this multi peptide approach can be used in this proposal. In this previous (unpublished) trial, 2 cohorts of patients were evaluated using the proposed methods. (Responses are listed as absolute # of CD4 or CD8 T Lymphocytes Producing Cytokine or Positive for CD107a per 1×10^6 cells plated.) This readout shows the breadth of this analysis as both CD4 and CD8 tell cells are evaluated using multiple parameters (cytokine production signifying activation – IFN- γ , IL-2 and TNF- α) and lytic potential as measured by CD107a expression. Had only one peptide been used to analyze this immune response it is likely that many of these immune responders would not have been identified. (unpublished).

A positive “response” will be defined as increased CD107a expression or increased intracellular cytokine production for given antigen for CD4 or CD8 cells. For example, Participant #2 in Table 1 will be scored has having 5 responses (CD4: INFg, TNF and CD8: CD107a, INFg and TNF).

In order to give added weight to the spread antigens (MUC1 and Brachyury) they will be weighted 150% higher than PSA antigens. Thus, the scoring will be as follows:

For PSA:

1 point each of the four CD4 parameters (CD107a, IFN- γ , IL-2 and TNF- α) – max total of 4
 1 point each of the four CD8 parameters (CD107a, IFN- γ , IL-2 and TNF- α) – max total of 4
 Total possible score for PSA response is 8

For MUC1:

1.5 points each of the four CD4 parameters (CD107a, IFN- γ , IL-2 and TNF- α) – max total of 6
 1.5 points each of the four CD8 parameters (CD107a, IFN- γ , IL-2 and TNF- α) – max total of 6

Total possible score for PSA response is 12.

For Brachyury:

1.5 points each of the four CD4 parameters (CD107a, IFN- γ , IL-2 and TNF- α) – max total of 6

1.5 points each of the four CD8 parameters (CD107a, IFN- γ , IL-2 and TNF- α) – max total of 6

Total possible score for PSA response is 12.

5.1.3 Flow Cytometry Analysis of Immune subsets (Biomarker Development)

As part of the extensive immune interrogation, peripheral immune cells will be evaluated by 30 markers to assess 127 immune subsets. ([Table 2](#)) This methodology has been previously described [43]. This added analysis will provide preliminary data to develop a Peripheral Immunoscore based on the frequency of specific pre-determined immune cell subsets in the blood of participants prior to therapy. The score is calculated from the changes in frequency of certain immune cell subsets after vaccine treatment. The resultant panel of markers would reflect immune response to the vaccine.

Table 2. Analysis of Peripheral Immune Cells

- A. **CD4:** Helper T lymphocytes (32 subsets)
- B. **CD8:** Cytotoxic T lymphocytes (29 subsets)
 - a. **Markers of PD-1 pathway and T cell activation (in CD4 and CD8):**
 - i. **EOMES:** activation
 - ii. **TCR- $\alpha\beta$:** activation
 - iii. **Tbet:** activation
 - iv. **BATF:** activation/exhaustion
 - b. **Maturation status of T lymphocytes (in CD4 and CD8):**
 - i. **Naïve:** CD45RA⁺ CCR7⁺
 - ii. **Effector Memory:** CD45RA⁻ CCR7⁺
 - iii. **Terminal (EMRA):** CD45RA⁺ CCR7⁻
 - c. **T lymphocyte markers (in CD4 and CD8):**
 - i. **CTLA-4:** inhibition
 - ii. **PD-1:** activation/inhibition
 - iii. **PD-L1:** activation/cross-inhibition
 - iv. **TIM-3:** inhibition
 - v. **ICOS:** activation (only on CD4)
- C. **Tregs:** Regulatory T lymphocytes (CD4⁺ CD25⁺ FoxP3⁺ CD127⁻) (7 subsets)
 - a. **CD45RA:** Tregs highly expandable *in vitro*
 - b. **CTLA-4:** Treg suppression
 - c. **CD49d:** “contaminating” effector lymphocytes (non-Tregs)
 - d. **ICOS:** Treg suppression
 - e. **PD-1:** activation/inhibition
 - f. **PD-L1:** cross-inhibition
- D. **B lymphocytes:** CD19⁺ (5 subsets)
 - a. **CTLA-4:** inhibition
 - b. **TIM-3:** inhibition
 - c. **PD-1:** activation/inhibition
 - d. **PD-L1:** cross-inhibition
- E. **NK:** Natural killer cells (CD56⁺ CD3⁻) (20 subsets)
 - a. **CD16⁺ CD56^{br}:** Functional intermediate, lytic and cytokine production
 - b. **CD16⁺ CD56^{dim}:** Mature NK, cytokine production
 - c. **CD16⁻ CD56^{br}:** Immature, abundant in human placenta
 - d. **CD16⁻ CD56^{dim}:** non-lytic, non-cytokine production
 - e. **TIM-3:** activation
 - f. **PD-1:** activation/inhibition
 - g. **PD-L1:** cross-inhibition
- F. **NK-T:** CD56⁺ CD3⁺ (4 subsets)
 - a. **TIM-3:** activation
 - b. **PD-1:** activation/inhibition
 - c. **PD-L1:** cross-inhibition
- G. **cDCs (Conventional DCs):** CD3⁻CD56⁻ CD1c⁺CD303⁻ (5 subsets)
- H. **pDCs (plasmacytoid DCs):** CD3⁻CD56⁻CD1c⁻CD303⁺ (5 subsets)
 - a. **Markers of DC activation**
 - i. **CD83:** activation
 - ii. **TIM-3:** inhibition
 - iii. **PD-1:** activation/inhibition
 - iv. **PD-L1:** cross-inhibition
- I. **MDSCs:** Myeloid-derived suppressor cells (CD11b⁺ HLA-DR^{low/-} CD33⁺) (20 subsets)
 - a. **CD14:** Common Myeloid Marker (high in monocytes, dim in granulocytes)
 - b. **CD15:** Granulocyte marker
 - c. **CD16:** most immature monocytic MDSCs
 - d. **PD-1:** activation/inhibition
 - e. **PD-L1:** cross-inhibition

5.1.4 MRI study

If logistically feasible, an MRI will be performed at baseline before the first vaccine administration and after the last vaccine administration as part of the pre-operative workup in the neoadjuvant cohort. This will be done to assess for changes in the imaging characteristics of the prostate cancer pre and post vaccination.

Prior to entering the scanner, the participant will answer the standard MRI safety checklist administered to all participants undergoing MRI in the Clinical Center to ensure that it is safe to perform an MRI. Images will be reviewed for lesions suspicious for prostate cancer. Pre and post-vaccine images will be compared to assess for changes seen on MRI. These studies will be performed by the NCI Molecular Imaging Program.

5.1.5 Additional Assays

Blood and tissue samples may be used for additional research studies, which may include phenotypic and functional analysis of tumor and immune-cell subsets (such as the CD3, CD4, and CD8 subsets and CD4:CD8 ratio), Class II immune responses, CTL assay, TBNK and analyses for cytokines (IFN- γ , IL-10, IL-12, IL-2, IL-4, etc.), chemokines, antibodies, tumor associated antigens, tumor specific gene expression profiling using RT-PCR of the RNA extracted from the tumor and/or other markers, and clonality score. Many of these studies will aid in not only assessing response, but predictors of response. If additional analyses beyond those already described above are planned, the protocol will be amended to address them.

[figure not shown]
All samples will be labeled with the following identifier system.

- Participant's enrollment #
- Trial number
- Participant's initials Example: 01-ABC

These labels are used only to send the samples from the NIH Clinical Center to the NCI Frederick Central Repository. The NCI Repository will process all samples, appropriately discard the label on the blood tube, and then store the samples with unique identifiers, to which only NCI study personnel will have the code to link to participant specific clinical information. Samples will be tracked according to Section [5.2](#).

5.1.6 Analysis of pre and post treatment samples

5.1.6.1 Pre and post treatment samples will be coded and analysis of tissues using multiplexed immunofluorescence or multispectral imaging to identify specific markers, including markers of immune cell subsets, may be performed in collaboration with:

PerkinElmer
[name]
[name]

Abbreviated Title: Prostvac-Nivo in prostate ca

Version Date: 01.10.2023

and

General Electric (GE) Global Research

Lifesciences and Molecular Diagnostics Org
[name]
[name]
[name]

5.1.6.2 Scanned images and/or tissue samples and linked, coded data (clinical parameters, outcomes data, laboratory data, and other relevant data) may be sent to Definiens for analysis to explore the tumor microenvironment and the impact of treatment. The Definiens tissue phenomics platform allows for quantitative histopathology and spatial pattern analysis of scanned images of tissue samples, and correlation of results with outcomes and clinical parameters.

Definiens

[name]
[name]

5.1.6.3 DNA and RNA-based analysis and quantitative proteomics may be performed in collaboration with:

5.1.6.3.1 *HTG Molecular Diagnostics, Inc.*

HTG Molecular Diagnostics, Inc.
[name]
[name]
[contact]
[contact]

HTG Molecular Diagnostics, Inc. has a platform to obtain RNA from formalin-fixed and paraffin-embedded (FFPE) tissues and from PBMC cells. NCI would send HTG Molecular paired coded samples of pretreatment and post treatment PBMC and FFPE slides (H&E and serial unstained slides) for sequencing analysis.

Correlative analysis may be planned at a later point in conjunction with [name] at UCSF who is doing a study in a similar participant population with a different design and different agents (PROSTVAC vs combination) to allow for a better ability to compare across studies.

Abbreviated Title: Prostvac-Nivo in prostate ca

Version Date: 01.10.2023

5.1.6.3.2 NantOmics

NantOmics
[name]
[name]

NantOmics performs comprehensive molecular profiling of samples through whole genome sequencing, whole transcriptome sequencing, and quantitative proteomics. Coded tissue and blood samples may be sent for analysis.

5.1.6.3.3 Certificate of Confidentiality

As part of study efforts to provide confidentiality of subject information, this study will obtain a Certificate of Confidentiality which helps to protect personally identifiable research information. The Certificate of Confidentiality allows investigators on this trial to refuse to disclose identifying information related to the research participants, should such disclosure have adverse consequences for subjects or damage their financial standing, employability, insurability or reputation. The informed consent includes the appropriate coverage and restrictions of the Certificate of Confidentiality.

5.1.6.3.4 Management of Results

Subjects will be contacted if a clinically actionable gene variant is discovered. Clinically actionable findings for the purpose of this study are defined as disorders appearing in the American College of Medical Genetics and Genomics recommendations for the return of incidental findings that is current at the time of primary analysis. (A list of current guidelines is maintained on the CCR intranet:

<https://ccrod.cancer.gov/confluence/display/CCRCRO/Incidental+Findings+Lists>). Subjects will be contacted at this time with a request to provide a blood sample to be sent to a CLIA certified laboratory. If the research findings are verified in the CLIA certified lab, the subject will be offered the opportunity to come to NIH (at our expense) to have genetic education and counseling to explain this result. If the subject does not want to come to NIH, a referral to a local genetic healthcare provider will be provided (at their expense).

This is the only time during the course of the study that incidental findings will be returned. No interrogations regarding clinically actionable findings will be made after the primary analysis.

5.1.7 Circulating Tumor Cells (CTC)

Rationale of investigation:

- Methods are in development for the purification and analysis of circulating tumor cells (CTC).
- One of these novel CTC technologies, developed by Epic Sciences, is summarized as follows: whole blood is aliquoted onto slides, nucleated peripheral blood cells are attached to

slides and examined, cytokeratin-positive/CD45-negative cells with an intact nucleus and a malignancy-consistent morphology are identified as CTCs, and their exact positions on the slides recorded. This technology has the advantage of being able to identify cells that may be CTC but cytokeratin negative. Since positive or negative selection is not needed, all circulating cells are captured and analyzed via proprietary technology, to include multiplex analysis.

- The evaluation of CTCs may give valuable insight into how treatment affects changes in CTC quantity and phenotype, such as AR splice variants, and how such changes are associated with clinical outcomes.

Blood collection:

At baseline and at one later timepoint (as close as possible to the time of planned prostatectomy or week 9 for initial safety cohort), one 10 mL Streck Cell-Free DNA (brown-black top) tube will be collected. [name] lab will be paged at [name] for tube pick up and shipping via FedEx Priority Overnight to Epic Sciences. These samples will be sent in ambient shippers provided by Epic Sciences to keep samples at room temperature. Alternatively, PBMCs collected and stored at -80°C for immunology assays may also be shipped to Epic Sciences for CTC analysis. Samples will be shipped to the following address:

Epic Sciences

[name]
[name]

5.2 SAMPLE STORAGE, TRACKING AND DISPOSITION

Samples will be ordered in CRIS and tracked through a Clinical Trial Data Management system. Should a CRIS screen not be available, the CRIS downtime procedures will be followed. Samples will not be sent outside NIH without appropriate approvals and/or agreements, if required.

5.2.1 Samples Managed by [name] Processing Core (BPC)

All samples processed by the Blood Processing Core (BPC) will be barcoded, with data entered and stored in the Labmatrix utilized by the BPC. This is a secure program, with access to Labmatrix limited to defined [name] lab personnel, who are issued individual user accounts. Installation of Labmatrix is limited to computers specified by [name]. These computers all have a password restricted login screen.

Labmatrix creates a unique barcode ID for every sample and sample box, which cannot be traced back to participants without Labmatrix access. The data recorded for each sample includes the participant ID, name, trial name/protocol number, time drawn, cycle time point, dose, material type, as well as box and freezer location. Participant demographics associated with the clinical center participant number are provided in the system. For each sample, there are notes associated with the processing method (delay in sample processing, storage conditions on the ward, etc.).

Barcoded samples are stored in barcoded boxes in a locked freezer at either -20 or -80°C according to stability requirements. These freezers are located onsite in the BPC and offsite at NCI Frederick Central Repository Services in Frederick, MD. Visitors to the laboratory are required to be accompanied by laboratory staff at all times. Access to stored clinical samples is restricted. Samples will be stored until requested by a researcher named on the protocol. All requests are monitored and tracked in Labmatrix. All researchers are required to sign a form stating that the samples are only to be used for research purposes associated with this trial (as per the IRB approved protocol) and that any unused samples must be returned to the BPC. It is the responsibility of the NCI Principal Investigator to ensure that the samples requested are being used in a manner consistent with IRB approval.

5.2.2 Samples Sent to Clinical Services Program (CSP)

All data associated with participant samples is protected by using a secure database. All Clinical Support Laboratory Staff receive annual training in maintaining records' confidentiality. All samples drawn at the NIH Clinical Center will be transported to the Clinical Support Laboratory at the Frederick National Laboratory for Cancer Research by couriers.

Samples will be tracked and managed by the Central Repository database, where there is no link to personal identifiable information. All samples will be stored in either a -80°C freezer or vapor phase liquid nitrogen. These freezers are located at NCI Frederick Central Repository in Frederick, Maryland.

NCI-Frederick Central Repositories (managed under a subcontract) store, among other things, biological specimens in support of NIH clinical studies. All specimens are stored in secure, limited access facilities with sufficient security, back up and emergency support capability and monitoring to ensure long-term integrity of the specimens for research.

Specimens are stored in accordance with applicable HHS and FDA Protection of Human Subjects Regulations in accordance with the subcontractor's Federal-wide Assurance. The subcontractor's role is limited to clinical research databases and repositories containing participant specimens. The subcontractor does not conduct nor has any vested interest in research on human subjects, but does provide services and support the efforts of its customers, many of which are involved in research on human subjects. The subcontractor's IRB reviews policies and procedures for labeling, data collection and storage, access, and security. The IRB will review protection of privacy issues prior to acceptance of any new work and in the event of change impacting privacy issues in existing work.

It is the intent and purpose of the subcontractor to accept only coded, linked samples and sample information. To the limit of our ability, every effort will be made to ensure that protected information is not sent electronically or by hard copy or on vial labels.

Sample data is stored in the BioSpecimen Inventory System II (BSI). This inventory tracking system is used to manage the storage and retrieval of specimens as well as maintain specimen data. BSI is designed for controlled, concurrent access. It provides a real-time, multi-user environment for tracking millions of specimens. The system controls how and in what order database updates and searches are performed. This control prevents deadlocks and race conditions. For security, BSI has user password access, three types of user access levels, and 36 user permissions (levels of access) that can be set to control access to the system functions. BSI

provides audit tracking for processes that are done to specimens including shipping, returning to inventory, aliquoting, thawing, additives, and other processes. BSI tracks the ancestry of specimens as they are aliquoted, as well as discrepancies and discrepancy resolution for specimens received by the repository. If a specimen goes out of the inventory, the system maintains data associated with the withdraw request. Vials are labeled with a unique BSI ID which is printed in both eye readable and barcoded format. No participant specific information is encoded in this ID.

Investigators are granted view, input and withdraw authority only for their specimens. They may not view specimen data or access specimens for which they have not been authorized. Access to specimen storage is confined to repository staff. Visitors to the repositories are escorted by repository staff at all times.

5.2.3 Protocol Completion/Sample Destruction

Once primary research objectives for the protocol are achieved, intramural researchers can request access to remaining samples, provided they have an IRB-approved protocol and participant consent.

Samples and associated data will be stored permanently unless the participant withdraws consent. If the participant withdraws consent the participant's data will be excluded from future distributions, but data that have already been distributed for approved research use will not be able to be retrieved. The PI will record any loss or unanticipated destruction of samples as a deviation. Reporting will be per the requirements of section [7.2.1](#).

6 DATA COLLECTION AND EVALUATION

6.1 DATA COLLECTION

The PI will be responsible for overseeing entry of data into a 21 CFR Part 11- compliant data capture system provided by the NCI CCR and ensuring data accuracy, consistency and timeliness. The principal investigator, associate investigators/research nurses and/or a contracted data manager will assist with the data management efforts. Primary and final analyzed data will have identifiers so that research data can be attributed to an individual human subject participant.

All adverse events, including clinically significant abnormal findings on laboratory evaluations, regardless of severity, will be followed until return to baseline or stabilization of event.

Document AEs from the first study intervention, Study Day 1, through 30 days after the subject received the last study drug administration. Beyond 30 days after the last study drug and through approximately 100 days, only adverse events which are serious and related to the study intervention need to be recorded.

An abnormal laboratory value will be recorded in the database as an AE **only** if the laboratory abnormality is characterized by any of the following:

- Results in discontinuation from the study
- Is associated with clinical signs or symptoms
- Requires treatment or any other therapeutic intervention

Abbreviated Title: Prostvac-Nivo in prostate ca

Version Date: 01.10.2023

- Is associated with death or another serious adverse event, including hospitalization.
- Is judged by the Investigator to be of significant clinical impact

If any abnormal laboratory result is considered clinically significant, the investigator will provide details about the action taken with respect to the test drug and about the participant's outcome.

End of study procedures: Data will be stored according to HHS, FDA regulations and NIH Intramural Records Retention Schedule as applicable.

Loss or destruction of data: Should we become aware that a major breach in our plan to protect subject confidentiality and trial data has occurred, this will be reported expeditiously per requirements in section **7.2.1**.

- Eligible participants must be confirmed and checklist completed. Consent form must be signed prior to registration with Central Registration Information Services.
- Data will be secured in study database. Data will be collected using protocol-specific case report forms and verified for accuracy and completeness. Hard copies of data will be stored in locked secured areas and data will be entered onto a secured electronic data base. The following protocol-specific study forms will be complete and stored: eligibility checklist (developed by Central Registration Office, CRO). A copy of all serious AE forms will be kept in the research record.
- Treatment is given according to protocol (dated notes about doses given, complications, and clinical outcomes).
- Toxicity is assessed according to protocol (laboratory report slips, etc.)
- Response is assessed according to protocol (X-ray, scan, lab reports, and date noted on clinical assessment, as appropriate).
- Drug Accountability Records are kept for each participant.

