3 STUDY IMPLEMENTATION

3.1 STUDY DESIGN

3.1.1 Rationale for Serial Cohort Design

The primary focus of this study will be to evaluate PROSTVAC and nivolumab in the neoadjuvant setting. However, given the concern that treating with these agents prior to radical prostatectomy may delay or compromise definitive radical prostatectomy (due to systemic adverse events or local inflammation) we will have a lead-in cohort evaluating the safety and tolerability of this combination in the castration resistant setting.

Participants in this initial cohort will be enrolled not more than 3 a week.

Following this lead-in cohort in the CRPC setting, we propose a cohort in the neoadjuvant setting evaluating the combination of PROSTVAC and nivolumab.

Abbreviated Title: Prostvac-Nivo in prostate ca

Version Date: 01.10.2023

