3.8 FOLLOW-UP EVALUATIONS

After subjects have stopped taking the study medication for any of the reasons listed in Section **3.6**, they will be seen at NIH, if logistically feasible, for a safety visit within 4-5 weeks for Lead-in mCRPC cohort and 6-8 weeks for neoadjuvant cohort of drug discontinuation. The safety assessments may be performed by a local physician and laboratory if participants unable to return to the NIH Clinical Center at this time.

The following assessments will be performed at the follow up safety visit:

- History and Physical Examination
- CBC with differential and platelet count, prothrombin time/INR, activated partial thromboplastin time
- Serum chemistries (Na+, K+, Cl-, CO2, BUN, creatinine, glucose, AST/ALT, bilirubin, calcium, phosphorous, albumin, magnesium, alkaline phosphatase, LDH, ionized calcium, amylase, lipase, total protein, uric acid), TSH
- Serum PSA level
- Adverse event reporting

After the safety visit, if there are no unresolved grade 3 or higher AEs, we will offer participants the opportunity to enroll on our long term follow up study. If there are unresolved grade 3 – 4 AEs, participants will be followed either at the NIH Clinical Center or by their local physician. In the latter case, we will obtain the physician's record of AEs.

Any scans performed outside of the NIH will also be obtained when possible.

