8.4.2 Bristol-Myers-Squibb

To be sent by OSRO, CCR, NCI, NIH:

Following the subject's written consent to participate in the study, all SAEs, whether related or not related to study drug, must be collected, including those thought to be associated with protocol-specified procedures. All SAEs must be collected that occur within 100 days of discontinuation of dosing.

All SAEs must be collected that occur during the screening period. If applicable, SAEs must be collected that relate to any protocol-specified procedure (e.g., a follow-up skin biopsy). The investigator should report any SAE that occurs after these time periods that is believed to be related to study drug or protocol-specified procedure.

SAEs, whether related or not related to study drug, and pregnancies must be reported to BMS within 24 hours. SAEs must be recorded on BMS or an approved form; pregnancies on a Pregnancy Surveillance Form.

SAE Email Address: [contact]

Abbreviated Title: Prostvac-Nivo in prostate ca

Version Date: 01.10.2023

SAE [contact]

If only limited information is initially available, follow-up reports are required. (Note: Follow-up SAE reports should include the same investigator term(s) initially reported.)

If an ongoing SAE changes in its intensity or relationship to study drug or if new information becomes available, a follow-up SAE report should be sent within 24 hours to the BMS (or designee) using the same procedure used for transmitting the initial SAE report.

All SAEs should be followed to resolution or stabilization.

The Investigator will ensure that all SAEs in the clinical database are reported to BMS and any applicable health authority during the conduct of the study. This reconciliation will occur at least quarterly and be initiated by the investigator. Investigator will request a reconciliation report from: [contact]. During reconciliation, any events found to not be reported previously to BMS must be sent to [contact].

BMS will be provided with a simultaneous copy of all adverse events filed with the FDA.

SAEs should be reported on MedWatch Form 3500A, which can be accessed at: <http://www.accessdata.fda.gov/scripts/medwatch/> or CCR SAE report form.

All SAEs should simultaneously be faxed or e-mailed to BMS at:

Global Pharmacovigilance & Epidemiology

Bristol-Myers Squibb Company

[contact]

Email: [contact]

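### Section 6.1 restricts adverse-event recording from 30 days after the last dose, which contradicts Section 8.4.2 on unrelated SAEs, ends before the neoadjuvant safety visit, and shortens post-operative recording as surgery is delayed

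*Combined protocol and SAP*

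**What the plan says.** Section 6.1 sets the recording period: "Document AEs from the first study intervention, Study Day 1, through 30 days after the subject received the last study drug administration". After that, and up to about 100 days, "only adverse events which are serious and related to the study intervention need to be recorded". The same section says that adverse events of any severity "will be followed until return to baseline or stabilization of event".

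Section 8.4.2, on reporting to the nivolumab supplier, is wider. From written consent, "all SAEs, whether related or not related to study drug, must be collected, including those thought to be associated with protocol-specified procedures". Its end point is equally plain: "All SAEs must be collected that occur within 100 days of discontinuation of dosing".

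Three other places bear on the point:

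- Section 8.2 refers to 6.1 for the recording timeframe.
- Section 3.8 brings participants back "for a safety visit within 4-5 weeks for Lead-in mCRPC cohort and 6-8 weeks for neoadjuvant cohort of drug discontinuation", and lists adverse-event reporting at that visit with no limit by seriousness or relationship.
- The neoadjuvant calendar (Section 3.5.2, footnote 4) schedules an SAE assessment about 100 days after nivolumab stops, also with no relationship limit. Footnote 9 of the lead-in calendar (Section 3.5.1) does the same.

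Safety in the localized cohort is a secondary objective (Section 1.1.2). Section 3.1.1 explains the lead-in cohort by the worry that treatment "may delay or compromise definitive radical prostatectomy (due to systemic adverse events or local inflammation".

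**The concern.** Two sections give different answers to a basic question: is an SAE that starts 31 to 100 days after the last dose, and is judged unrelated, recorded or not? Under 6.1 it need not be. Under 8.4.2 it must be. If staff follow 6.1, capture of a late SAE depends on one investigator's attribution in a trial without a concurrent control.

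The second difficulty is the anchor. In the neoadjuvant cohort the event most likely to generate adverse events after dosing is the prostatectomy, yet the window counts from the last dose. A man whose surgery slips, or whose dosing stops early while surgery stays where it was, gets the shortest period of full post-operative recording. Those are the men in whom delayed or compromised surgery, the worry in Section 3.1.1, would be of most interest.

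**Working it through.** The plan states no figure to reproduce. The check is a comparison of the texts followed by calendar arithmetic.

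**Comparison of the recording rules**

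| Source | Start | To 30 days after last dose | 31 to about 100 days |
|---|---|---|---|
| 6.1 | First study intervention | All AEs | Serious and related only |
| 8.4.2 | Consent | All SAEs | All SAEs, related or not |
| 3.8 (neoadjuvant visit) | n/a | n/a | AE reporting, no limit stated |
| 3.5.2, footnote 4 | n/a | n/a | SAEs, no relationship limit |

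The rules differ on unrelated SAEs from day 31 to day 100, and on SAEs between consent and first treatment. Section 8.2 says that events in the collection period are documented whatever their relationship, but takes that period from 6.1, so it does not settle the matter.

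**Inputs.** With full dosing, the last neoadjuvant dose is at week 8, day 56 (Sections 2.2.1 and 3.1.2). Surgery is allowed from week 5 to week 12, ideally near week 9 (Section 4; Section 3.5.2, footnote 5). The safety visit is 42 to 56 days after the last dose (Section 3.8).

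**Formula.** With last dose on day D and surgery on day S, full recording ends on day D + 30. The fully recorded post-operative days are max(0, D + 30 − S).

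| Last dose | Surgery | D + 30 | S | Fully recorded post-operative days |
|---|---|---|---|---|
| Week 8 | Week 9 | 86 | 63 | 23 |
| Week 8 | Week 10 | 86 | 70 | 16 |
| Week 8 | Week 11 | 86 | 77 | 9 |
| Week 8 | Week 12 | 86 | 84 | 2 |
| Week 4 | Week 5 | 58 | 35 | 23 |
| Week 6 | Week 9 | 72 | 63 | 9 |
| Week 4 | Week 9 | 58 | 63 | 0 |

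After a week-8 dose, coverage reaches zero at day 86, and 86 / 7 = 12.3 weeks.

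**Safety visit.** In the neoadjuvant cohort it falls 42 − 30 = 12 to 56 − 30 = 26 days after full recording ends. After a week-8 dose that is study day 98 to 112. In the lead-in cohort (4-5 weeks, days 28 to 35) the visit straddles the limit, from 2 days before it to 5 days after, so the mismatch is mainly a neoadjuvant one.

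**SAE limit in 8.4.2.** One hundred days after a week-8 dose is day 156, which is post-operative day 156 − 63 = 93 for week-9 surgery and 156 − 84 = 72 for week-12 surgery.

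**The case against.** A reader might infer that most post-operative complications would go unrecorded. The documents do not support that. On the intended schedule the first 23 post-operative days are fully recorded, and events that start in that time are followed until they resolve or stabilize. Nothing in the documents gives the timing of complications, so no share can be put on what is missed. Coverage falls to 2 days only at the edge of the permitted surgical window, and to zero only with surgery beyond that window or with early cessation of dosing and surgery not moved forward.

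It is also tempting to say that post-operative complications are the trial's own stated worry. Section 3.1.1 names delay or compromise of the prostatectomy. Complications could reflect compromised surgery, but the section does not name them.

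Nor can one say that unrelated SAEs will be lost, or that safety will look better than it was. Section 6.1 sets a minimum and does not forbid recording more, and 8.4.2 and the calendar footnote both call for SAEs to about 100 days. What the documents show is an unresolved inconsistency. The mismatch with the safety visit is likewise a poor fit and not a flat contradiction.

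Finally, 8.4.2 might be read as governing only reports to the supplier, with 6.1 governing the trial database. That does not remove the problem, because the quarterly reconciliation in 8.4.2 works from SAEs in the clinical database. An unrelated late SAE that 6.1 leaves out would not be found there.

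**Conclusion.** The plan is wrong as written on two counts. Sections 6.1 and 8.4.2 contradict each other on unrelated SAEs from day 31 to day 100 after the last dose, and nothing else resolves it. Full adverse-event recording also stops 12 to 26 days before the neoadjuvant safety visit, so a new event found there that is non-serious or judged unrelated need not be recorded under 6.1.

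After a week-8 last dose, full post-operative recording is 23 days for week-9 surgery, 2 days for week-12 surgery and none after about week 12.3. The shrinkage with delay weakens the secondary safety objective in the localized cohort. It does not touch the primary T-cell comparison. The day counts use nominal visit days and ignore the ±3-day dosing windows. How many men would be affected depends on the actual surgery dates, which the plan cannot show.

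**What to change.** Amend 6.1, and the pointer to it in 8.2, so that:

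- all SAEs, regardless of relationship, are recorded from consent to 100 days after the last dose, matching 8.4.2 and the calendar footnotes; and
- all adverse events in the neoadjuvant cohort are recorded through the 6-8 week safety visit.

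After a week-8 dose, full recording would then run to day 98-112. That is 35 to 49 post-operative days for week-9 surgery (98 − 63 to 112 − 63) and 14 to 28 for week-12 surgery (98 − 84 to 112 − 84).

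The cost is modest extra data entry, since the visit and the 100-day contact already exist. Records may have to be requested where surgery is done at an outside institution, which Section 4 allows. A fixed 30-day post-operative period is not proposed: for week-12 surgery it would run to day 84 + 30 = 114, past the latest safety visit on day 112, and the documents give no basis for that length.

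Optionally, and separately from the recording window, report descriptively how many men had prostatectomy after week 12 or not at all. The trial already has the surgery dates.
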